The long term goal of the research is to develop non-invasive brain stimulation as an evidence-based tool to facilitate abstinence during the first week after a quit attempt, as this is a robust predictor of 6-month treatment outcomes with traditional pharmacotherapeutic and behavioral interventions. The next step in pursuit of that goal is to systematically and parametrically evaluate the efficacy of two promising TMS treatment strategies (LTP-like stimulation to the mPFC (Aim 1), LTP-like stimulation to the dIPFC (Aim 2)) as tools to change smoking behavior and brain reactivity to smoking cues. These aims will be addressed in serial (Aim 1 Years 1-3, Aim 2 Years 3-5). A randomized, double-blind, sham-controlled design will be used for each aim. In total, 138 smokers will be recruited from the tri-county area surrounding Winston-Salem, NC. Current cigarette smokers seeking to quit smoking and willing to set a quit date will be recruited from the tri-county area using digital and print advertising in diverse media outlets. Following informed consent and screening, participants will be randomized to receive real or sham TMS to the mPFC (Aim 1, Years 1-3) or the dlPFC (Aim 2, Years 3-5) (see Table 1 and TMS Procedures below for more details regarding sham controls and double blinding procedure). During the Treatment Phase, participants will receive 10 sequential days of TMS (with additional behavioral and MRI scanning (see Table 1). Participants will receive TMS at least 3 times a week for a total of 10 TMS sessions. During the follow-up phase, participants will receive 4 maintenance TMS sessions once a week for 4 weeks. During the Follow Up Phase, behavioral assessments will be acquired weekly for the first 4 weeks (see Table 2), and daily EMA will be acquired. Consistent with the CNDS model, the primary hypotheses are that LTP-like stimulation to the mPFC and LTP-like stimulation to the dlPFC will both lead to a decrease in

smoking cue-reactivity in the salience network (neuroimaging outcome), and cigarette value (behavioral outcome) but that directly targeting the value circuit (mPFC) will be more efficacious. Additionally, we will test the hypothesis that individuals with higher discounting rates and cigarette valuation at baseline will respond more to the stimulation strategies compared to those with lower baseline discounting and valuation (Exploratory Aim).

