Study Visit Procedures: At all visits, individuals will provide a urine screen to detect recent use of drugs of abuse and pregnancy, a breath carbon monoxide (CO) sample to detect recent cigarette smoking, and a breath sample to test for recent alcohol use. During the consent visit, visits 1, 6, 10 and follow up visits samples will be collected to determine cotinine (nicotine metabolites) levels in the urine. Samples will be taken from the urine sample provided for the drugs of abuse screen, no additional samples will be required from the participant. At visits 1, 6, 10 and follow up visits (Assessment visits), participants will complete a battery of behavioral assessments following active TMS or sham (see Table 2). MRI scanning (at visits 1 and 10) will occur prior to TMS in order to isolate cumulative, rather than acute, effects of TMS. At all visits participants will be required to provide a CO reading at least 50% of their baseline CO measure to ensure they are at least 6 hours deprived from cigarettes. Cigarette deprivation will be use to increase craving and responding for cigarettes. Short term cigarette deprivation has known amplification effects on the brain response to smoking cues (93, 94). Moreover, we have extensive experience with successfully using this deprivation procedure (33, 41).

Table 2 1. Biochemical and self-report assessment of tobacco use and dependence						
Measure	Time (Min.)	Visits	Description			
Carbon monoxide (CO Level)	1	1-10, and follow-ups	Breath CO provides an accurate measure of recent exposure to CO , including from smoking combustible tobacco products (95). The CO measurement will be used to determine recency of smoking.			
Timeline Follow-Back (TLFB) interview	5	1, 6, 10, and follow-ups	This self-reported tobacco product use interview asks participants to retrospectively estimate the number of tobacco products they've used each day for the past 30 days or since the previous assessment, whichever is fewer (89).			
Fagerström (FTND)	3	1, 6, 10, and follow-ups	This 6-item questionnaire quickly assesses degree of cigarette dependence (96, 97). Test for Cigarette Dependence.			
2. Measures of t	tobacco pr	oduct value an	d sensitivity (**PRIMARY DEPENDENT MEASURES)			

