- 2. Potential for scalp discomfort and headaches: Some people report mild discomfort when the magnetic pulses are applied over the scalp. A small number of people (~5%) report headache following rTMS. However, the headaches are temporary and manageable with common over-the-counter pain remedies.
- 3. Potential hearing loss: The TMS coil generates a high-energy click that may cause hearing damage. Humans exposed to TMS have shown temporary increases in auditory threshold (especially at high frequencies) lasting at least 5 minutes and less than 4 hours.
- 4. Safety in case of pregnancy: This protocol will exclude pregnant women. The risks of using TMS with pregnant women are currently unknown. Please inform the research team if you are pregnant or think that you might have become pregnant during the study. A pregnancy test will be performed before the experiment begins.
- 5. Potential for reflex syncopal event: Syncope is defined as a momentary loss of awareness and postural tone. It typically has a rapid onset, short duration, and spontaneous recovery. Although syncopal episodes are very rare with TMS (less than 1%), they typically occur during the motor

threshold procedure before the rTMS treatment has begun. Individuals that are sleep deprived and have low or unstable blood pressure are at greater risk.

6. Interaction with electrical or metal implants: Electrically, magnetically or mechanically activated implants (such as cardiac pacemakers), as well as clips on blood vessels in the brain may be affected by rTMS (as well as MRI) and cause pain or abnormal signal propagation. Therefore individuals that have these implants and devices or suspect that they may have pieces of metal in their eyes, head, or body (e.g. bullets, shrapnel, fragments from metallurgy) will be excluded from the study.

Adequacy of protection against risks

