- 1. Although the TMS protocol that we are using has never been associated with causing a seizure, individuals that have a history of seizures, stroke, or other neurological impairment that might lower their seizure threshold will be excluded from the study. All study personnel will have received a formal education course in seizure detection, care, and treatment and a physician will be available to immidiately assist in stabilizing the participants in the event of a seizure Any participant who has a seizure cannot continue with the study.
- 2. We will exclude individuals with claustrophobia such that they are not exposed to this risk. Additionally participants will be given a pressure sensitive squeeze ball that they can use to indicate at any time that they would like to leave the scanner.
- 3. To protect against hearing loss concerns, participants will wear high fidelity earplugs throughout the scanning session.

- 4. Participants will be informed of potential risk of scalp discomfort and headache before they consent and will be told that they should feel free to take non-steroidal antiinflammatory agents after the TMS session if they have a headache.We will also exclude individuals with chronic migraines such that they are not exposed to this risk.
- 5. We will exclude pregnant females such that they are not exposed to this risk.
- 6. All participants that enroll in this study will complete a written MRI saftey screen. We will also use a handheld metal detector to ensure the participant has no metal in or on is/her body before entering the MRI scanning room.

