Subject Recruitment Methods

Advertisements will be placed around campus in approved locations, especially at WFUHS clinics. Other ads will be submitted to local newspapers as well as internet advertising to reach the general population (e.g. Craigslist, broadcast messages at WFUHS). Recruitment will also occur at community events where recruitment materials (such as pens, backpacks, and mugs) will be handed out to individuals. Interested individuals will email, call, or text the research center and will then be contacted via telephone, phone screened, and scheduled for screening if eligible. If an individual declines study participation or is not eligible via phone screen, their information will be shredded and destroyed. Informed consent will be reviewed with the potential participant by a member of the key personnel on this visit. The consent will be signed by the participant as well as one of the Key Personnel on the proposal. A copy of the consent will be given to the subject and the original placed in the research record. The consent and HIPAA process will be done in [name] research laboratory and facility. The MRI scans will be done at the MRI center and the TMS sessions will be done in the TMS laboratory located in [name] research lab.

Additionally, a chart review will be conducted for research purposes. Potentially eligible participants will be identified. The potentially eligible participants in the PIs practice will be informed about the study as the PI feels is appropriate. Then potential participants who have agreed to be contacted for future research by logging their WFU Research Permissions preferences in MyChart will be contacted by phone and invited to participants. All other participants will be contacted through their providers to be informed of the study if the provider feels it is appropriate.

Informed Consent

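### The hearing hazard is attributed to the TMS coil, but the only written hearing protection is for MRI scans, so no TMS session is covered

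*Combined protocol and SAP*

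**What the plan says.** The hazard is described in Potential Risks, under the risks of repetitive TMS (Other potential risks, item 3): "The TMS coil generates a high-energy click that may cause hearing damage". The same item reports an observed effect: "Humans exposed to TMS have shown temporary increases in auditory threshold (especially at high frequencies) lasting at least 5 minutes and less than 4 hours". The separate list of MRI risks names no hearing risk.

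The safeguard is in Protection Against Risks, under the joint heading for MRI and TMS, item 3, which is aimed at hearing loss: "participants will wear high fidelity earplugs throughout the scanning session". No other hearing-protection measure appears in the supplied text.

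The schedule and setting come from three places:

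- Design: "Participants will receive TMS at least 3 times a week for a total of 10 TMS sessions", and during follow-up "participants will receive 4 maintenance TMS sessions once a week for 4 weeks".
- Study Visit Procedures: "MRI scanning (at visits 1 and 10) will occur prior to TMS".
- Subject Recruitment Methods: "The MRI scans will be done at the MRI center and the TMS sessions will be done in the TMS laboratory".

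The Sample Size section adds that, for COVID-related reasons, some participants will have no MRI.

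**The concern.** A protection section should answer the risk section item by item. Here the risk comes from one procedure and the protection is attached to another. Participants meet the named hazard repeatedly over the treatment phase, and the named protection is not required on those occasions. There is also an oversight problem. The Data and Safety Monitoring section has adherence to the protocol monitored by the IRB, and a precaution that is not in the protocol cannot be checked or recorded as a deviation if it is missed.

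**Working it through.** The plan gives no figure to reproduce here. The check is a comparison of texts followed by a count.

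**1. Could the scanning session include TMS?** No, for three reasons.

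- Place: scans are at the MRI center and TMS is in the TMS laboratory.
- Time: at the two visits with both, the scan comes before the stimulation.
- Usage: in the same protection list, item 2 uses the word scanner for the MRI, and item 4 refers separately to the TMS session when it discusses headache. The authors keep the two apart.

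**2. Is hearing protection required elsewhere?** The TMS Treatment section and the active-sham and blinding section describe the cap, coil position, motor threshold, ramping, electrodes and coil flipping. Neither mentions earplugs or any other hearing measure. The statement about following TMS safety guidelines sits under seizure risk and names none. The reference to the group's prior publications names none either.

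**3. Session count per participant.**

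| Procedure | Number | Written hearing protection |
|---|---|---|
| MRI scans (Visits 1 and 10) | 2, or 0 if MRI is skipped | Yes |
| TMS treatment sessions | 10 | No |
| TMS maintenance sessions | 4 | No |
| Motor-threshold determination | Before treatment at Visit 1 | No |

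Total TMS sessions are 10 + 4 = 14. Table 1, as it reads in the supplied text, marks TMS in the treatment phase only, so I give both totals. The written measure covers 0 of 10, or 0 of 14.

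**4. Exposure in pulses.** The TMS Treatment section states 1200 pulses per session. Its train parameters give a different number: 15 pulses per second × 2 seconds = 30 pulses per train, and 30 × 20 trains = 600. Both are carried through:

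- At 1200 per session: 1200 × 10 = 12,000, or 1200 × 14 = 16,800.
- At 600 per session: 600 × 10 = 6,000, or 600 × 14 = 8,400.

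By the same parameters a session lasts 20 × (2 + 8) = 200 seconds, of which 20 × 2 = 40 seconds is stimulation. Motor thresholding and ramping are not included.

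**5. Who is affected.** The active side of the coil faces the head during motor thresholding at the initial visit, whatever the assignment, so sham participants also receive real pulses then. Participants without MRI fall outside the clause entirely.

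**The case against.** The strongest reply is that this is a drafting slip. The protection list covers MRI and TMS jointly, hearing is item 3 in both lists, and MRI carries no hearing risk of its own in the protocol, so the earplugs were presumably meant for the TMS hazard. The group's Study 1 gave TMS inside the scanner, and wording carried over from such a protocol would explain the mismatch. That origin is plausible, though it is inference. It supports the correction, because the clause would then not say what was intended.

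The second reply is that actual practice cannot be judged from this text. The protocol appeals to safety guidelines, prior publications and staff training, and promises a published operating procedure. The consent pages were removed, and a sentence on TMS safety procedures is garbled in the supplied text. This stands: nothing here shows that participants would go unprotected, and the conclusion has to be confined to the written safeguard in the text supplied.

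Third, a session count does not measure harm. The only observed effect the protocol reports is temporary, and stimulation is brief. That also stands, although the protocol itself says damage is possible.

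Finally, a wear check refers to a session form the documents do not describe. It is a useful addition but not needed to close the gap.

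**Conclusion.** The concern holds. The protocol names a hearing hazard from the TMS coil and attaches its only written hearing safeguard to MRI scans. Coverage is at most 2 scans, none of the 10 to 14 TMS sessions, and no visit at all for participants who skip MRI. The size is in sessions left uncovered; the documents give no basis for estimating the probability of harm.

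The conclusion assumes that the removed consent pages and the operating procedure do not stand in for a protocol requirement. If they do mention earplugs, practice may be sound, but the protocol clause would still be wrong. The point should be corrected for participant safety. It does not affect sample size, power, type I error or the analysis.

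**What to change.** Reword item 3 of the MRI and TMS protections so that hearing protection is worn during every MRI scan, every motor-threshold procedure and every TMS session, including maintenance sessions. State that it applies equally to real and sham, so that earplug use cannot differ by assignment and hint at the allocation. Confirm that the consent form and operating procedure say the same.

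Optionally, add a tick-box to whatever record is kept at each TMS session, so that wear can be monitored.

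The cost is one phrase in a protocol amendment plus earplugs of the kind already specified for MRI. The tick-box, if adopted, is a small extra.

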1) Storing the unblinding spreadsheet on a secure server that is not accessible by members of the study team that are blinded

2) In the event of a safety event (and at the conclusion of the year), she will have the ability to look up the condition the participant was receiving (active/placebo)

3) A conflict of interest will be avoided by secondary evaluation of records by a Monitoring Entity (ME) (aka. data safety monitoring board- DSMB) on an annual basis. Quality control will include regular data verification (Integrity of the Consent and HIPAA, scores on assessments, MRI scanning information), study progress, subject status, adverse events, and protocol deviations. Protocol adherence will be monitored by the Wake Forest IRB, who will also be given access to the reports from the PI to the ME.

Provisions to Monitor the Data to Ensure the Safety of Subjects

DSM Board Plan: Meet annually with the PI to discuss the information listed in "Content of ME/DSM report". This content of this meeting will be formalized in a report which will be circulated by email and digitally approved by the PI and ME/DSMB. The approved report will be sent to the Wake Forest IRB, and to NIH.

Content of DSM Report: The following information will be included in the DSM report- number of individuals consented, number of individuals enrolled, number of active participants, gender and race distribution of subjects, discussion and listing of all amendments to the proposal, any publications and/or scientific presentations related to the proposal, update on any resolved or unresolved AE/SAEs, review of any new scientific literature related to the safety and efficacy of this protocol.

Plans for Interim Analysis of Efficacy Data: Data from this study will be analyzed when 20% increments of the recruitment goal have been obtained(e.g. 20% (n=27), 40% (n=55), 60% (n=83), 80% (n=110), 100% of the total enrolled sample (n=138)). A member of the DSMB that holds a copy of the unblinding key will provide the PI with the unblinding codes for individuals that have completed enrollment. Data analysis will be performed by trainees for educational purposes (e.g. graduate students, postdoctoral fellows) as well as the laboratory manager for preparation of DSMB reports and assessment of any disparities in the demographic distribution between the active and placebo groups. Final analysis will occur when all participants have finished the final follow-up phase of the study.

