Responsibility for Data and Safety Monitoring: The PI, protocol-approved research team, and ME/DSMB are all responsible for data and safety monitoring. The PI will be most involved in data and safety oversight. The PI will discuss data integrity and inquire about safety/participant tolerance in weekly meetings with the research team.

Data Entry Methods: Data will be collected using REDCapTM, which is a secure web application for building and managing online surveys and databases. REDcapTM supports online or offline data capture for research studies and operations. Participants and protocol-approved study personnel will enter data directly into the online portal to ensure security and prevent data loss.

Data Analysis Plan: Data for this study (behavioral assessments, functional MRI measurements) will be acquired by protocol-approved members of the research team, including graduate students and research specialists. These individuals will also perform data management and analysis under the guidance of the PI. Deidentified data will be shared per NIH requirements. Manuscript composition will be led by the PI and Co-Is, with the assistance of the research team.

Quality Assurance Plan: Weekly meetings will be held between the PIs and research team to discuss any data-related problems as well as qualitative comments received during data collection. Initial data analyses will examine distributions of variable scores, and comparability of baseline characteristics across conditions, any necessary adjustments to analyses will be made. Confidentiality protections are outlined below.

Review of the study will be conducted annually by the PI and laboratory manager (including enrollment, retention, assessment inventories) and discussed with the DSMB. Data collected in previous studies by our research group have demonstrated that after extended use in the MRI scanner environment (likely more than 5000 pulses) the strength of the induced magnetic field from the biphasic coil begins to drop in a non-linear fashion. Consequently, the intensity of the induced magnetic field from the coil will be assessed by protocol-approved study personnel and logged weekly (alongside with protocol use, number of pulses, intensity of pulses). This cumulative record of coil performance will be monitored and, when the intensity of the induced field had degraded 10%, we will switch to a new, identical coil.

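### The interim efficacy plan sends unblinding codes to the PI during recruitment, and after that nothing separates those who see by-arm data from those who run the trial

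*Combined protocol and SAP*

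**What the plan says.** The Design section calls each aim randomized, double-blind and sham-controlled. Under Data and Safety Monitoring, the part headed Plans for Interim Analysis of Efficacy Data says: "Data from this study will be analyzed when 20% increments of the recruitment goal have been obtained", with sizes 27, 55, 83, 110 and 138. It continues that a DSMB member who holds the key "will provide the PI with the unblinding codes for individuals that have completed enrollment".

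On who does the work: "Data analysis will be performed by trainees for educational purposes", "as well as the laboratory manager for preparation of DSMB reports and assessment of any disparities in the demographic distribution" between the groups. The sentence does not make clear whether the DSMB-report and demographic purposes limit the trainees' work or only the laboratory manager's. The same part ends: "Final analysis will occur when all participants have finished the final follow-up phase of the study".

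There is one safeguard. The key-holder's duties include "Storing the unblinding spreadsheet on a secure server that is not accessible by members of the study team that are blinded". The document does not say which team members those are.

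The Data Analysis Plan says that behavioral and fMRI data "will be acquired by protocol-approved members of the research team, including graduate students and research specialists", and that these same people manage and analyse the data under the PI's guidance. The Quality Assurance Plan sets weekly meetings of the PIs and the research team. Of the annual meeting between the DSMB and the PI, the DSM Board Plan says: "This content of this meeting will be formalized in a report which will be circulated by email and digitally approved by the PI" and the DSMB.

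**The concern.** A double-blind trial needs more than a blinded participant and device operator. People who direct staff, collect outcomes or decide how outcomes are modelled should not know by-arm results while the trial is running. Here the PI receives codes and guides staff who both collect and analyse.

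What is at stake is mainly the credibility of analysis choices. The Behavioral Outcomes section leaves the covariance structure to a comparison of AR(1), compound symmetry and a general form. It also lets plots decide whether time is categorical or continuous. The Analytical Plan allows further inferential analysis as appropriate. The Quality Assurance Plan allows analyses to be adjusted after score distributions and baseline comparability have been examined, without saying when or whether blinded. Once by-arm data are open, no one can later show that these choices were made without knowledge of the results.

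Staff expectation is a weaker and indirect route, because the primary behavioral measures are the participants' own responses.

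**Working it through.** **1. The plan's look sizes.** Inputs: recruitment goal 138 and 20% steps. 0.2 × 138 = 27.6, 0.4 × 138 = 55.2, 0.6 × 138 = 82.8, 0.8 × 138 = 110.4. The stated 27, 55, 83 and 110 agree to within one participant.

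**2. Where the looks fall.** Still to recruit: 138 − 27 = 111, 138 − 55 = 83, 138 − 83 = 55, 138 − 110 = 28. The aims run in series with 69 each (Design; Sample Size). The looks at 27 and 55 fall within Aim 1. Those at 83 and 110 fall after 83 − 69 = 14 and 110 − 69 = 41 participants of Aim 2. Both aims are exposed while they recruit.

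**3. Who can see what.**
- Codes: from the DSMB key-holder to the PI.
- Analysis: trainees and the laboratory manager; separately, the staff who acquire data also analyse it under the PI.
- Graduate students appear both as analysts of the interim data and as data collectors.
- Timing of release: completed enrollment, which differs from the completion of final follow-up used for the final analysis. Read literally, it could include people still in follow-up.
- Release at each look is the natural reading, but it is not stated.

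**4. Does looking inflate type I error?** For a model fixed in advance, with no look acted on or claimed, the final test keeps its 5%. The remaining question is what the open form of time contributes.

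Set-up: no true effect, visits on days 1, 6 and 10, 2:1 allocation, complete data, unstructured covariance, final n = 69 (one aim), group-by-time test at 5%. Categorical time uses Hotelling's test, F with 2 and n − 3 df. Linear time uses t with n − 3 df. As an illustration, suppose the form of time with the smaller p-value is kept for the final test (600,000 simulated trials):

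| Form of time | Type I error per outcome |
|---|---|
| Fixed in advance, either form | 5.0% |
| Chosen at n = 27 | 6.4% |
| Chosen at n = 55 | 7.2% |
| Chosen at the final analysis, no interim look | 7.5% |

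The last row is the largest, so this inflation comes from the open model and not from the looks.

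**5. Sensitivity to the baseline.** The Behavioral Outcomes section analyses change from baseline but also lists day 1 as an analysed visit. If visit 1 is the baseline, only days 6 and 10 carry change scores. With two time points, categorical and linear time give the same 1-df interaction test, there is nothing to choose between, and the figure is 5%. The range for this gap is therefore 5% to 7.5%.

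**6. Carry-over to Aim 2.** Aim 2 is to be evaluated in the same way as Aim 1, but in different participants. A model chosen on Aim 1 data is independent of Aim 2 data, so the Aim 2 test keeps 5%.

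**The case against.** The strongest reply is that the plan has real safeguards and that no error rate is shown to rise because of the looks.

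- A DSMB member holds the key on a restricted server. This stands, and a reader who inferred that the plan has no separation of roles at all would be wrong. The gap opens after release.
- The device procedure keeps participant and coordinator blind, and each participant has an individual number, so one person's code does not itself reveal another's arm. This stands. The documents do not support a claim that the device blind is directly broken.
- No interim test or efficacy stop is planned; Trial Stopping Rules concern serious adverse events only. This stands.
- The inflation in the working belongs to the open model and would exist without any look. This stands. Removing the looks alone would not lower it. Choosing by smallest p-value is also a worst case that the plan does not describe.
- The listed content of the DSM report includes no by-arm efficacy result. This stands, but it also means that the listed content does not require giving codes to the PI.
- The named uses are education, DSMB reports and demographic balance, and the text does not say outright that by-arm efficacy results go to the PI. However, the heading says efficacy, the PI holds the codes and the PI guides the analysis, so such results can reach the PI.

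None of this supplies the missing rule on who may see by-arm results after release.

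**Conclusion.** The concern holds as a gap in control of unblinded information. Followed as written, the plan lets by-arm data reach the PI and data collectors with up to 111 of 138 participants still to be recruited, and in both aims. The consequence is that open analysis choices can no longer be shown to have been made blind. This rests on reading the release as occurring at each look.

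A reader might infer that repeated looks push type I error well above 5%. If each look were tested at an unadjusted 5% and acted on, it would be about 10.2% per outcome in Aim 1 (looks at 27, 55 and 69) and 11.5% in Aim 2 (14, 41 and 69), assuming complete data. The plan describes no such testing, so these figures do not apply to it. Nor does a model carried from Aim 1 inflate error in Aim 2.

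The undefined form of time is a separate gap that compounds this one: 5% to 7.5% per outcome, depending on the baseline visit and on when the choice is made. With no added error shown from the looks themselves, I rate this as a should-fix.

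**What to change.** Delete the release of codes to the PI and the by-arm interim efficacy analyses. Have the key-holder send any by-arm safety and demographic tables to the DSMB only, in a closed report kept apart from the report that the PI approves. Keep both of the key-holder's look-ups (after a safety event and at year-end), with results not passed to blinded staff.

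Keep the PI, laboratory manager, trainees and data collectors blinded, working on pooled data, until that aim's final follow-up is complete and its data are locked. Use that point in place of completed enrollment.

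Before any code is released, fix the primary behavioral model: baseline visit, visits analysed, form of time, covariance structure and covariates. State that no efficacy claim or stopping decision will rest on interim data.

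Cost: protocol wording and one short model specification. Trainees lose early unblinded data, and the key-holder takes on a small table-making task. If that member cannot do it, an analyst outside the laboratory could. Participants, visits and sample size are unaffected.
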